- Collaboration with City Services (*City of Philadelphia IRB must approve study. For more information, go to <http://www.phila.gov/health/irb/>.*) *Please list collaborating city services:*
- Unaffiliated Investigators. *Each will need to complete an unaffiliated investigator agreement available on the OHR website. Please specify by name and role in study:*

2. This question is not applicable if research is a commercially sponsored multi-center trial.

Will research be conducted in states other than Pennsylvania? YES NO

If YES, does research involve subjects age 17 or younger? YES NO

If YES to either or both, in what state(s) will research be conducted? _____

Below please (a) verify the age at which participants in such state(s) have the ability to consent to participation in research, including any medical treatments or procedures, if applicable and/or (b) verify the requirements for determining who may serve as a Legally Authorized Representative, including a guardian for a child to participate in research. You must also provide information on any state specific regulations on privacy requirements and genetic research if applicable. Please contact the Privacy Office for information, as needed.

Age at which participants have the ability to consent to participate in research: _____

State specific requirements: _____

3. If the investigator is the lead investigator or Jefferson is the lead site in a multi-site study, please address the following: N/A

- a. Where is the repository for adverse events and unanticipated problems and how will information be disseminated to other sites?

663
664
665
666
667
668
669
670
671
672
673
674
675
676
677
678
679
680
681
682
683
684
685
686
687

- b. Who will tabulate and disseminate interim results?
- c. Who will provide information to other sites concerning protocol modifications?
- d. Describe how information that is relevant to participant safety will be managed (i.e., notifying site investigators of SAEs and Unanticipated Problems Involving Risks to Subjects or Others, communicating DSMB or Interim Reports, etc.)
- e. Is this study part of a cooperative single IRB submission? YES NO
 - a. If yes, please attach documentation of approval by the Federal department or agency supporting or conducting the research or lead institution as part of your submission. IRB approval will NOT be issued until documentation has been received.

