JEFFERSON—Office of Human Research

SUMMARY OF INTERVENTIONAL HUMAN SUBJECTS RESEARCH

Version Date – FOR OHR USE: 11/11/21

Please address all applicable points to create a complete and succinct synopsis of the protocol. If a point does not apply to your study, please state “NA.” Use language, insofar as is possible, that can be understood by a layperson, and provide meanings for all acronyms used. Please maintain all questions in the body of the text. For non-interventional research (questionnaires, surveys, and all sociobehavioral research), use form OHR-2B. **Form must be typewritten.**

PART A - SUMMARY OF STUDY

1. Brief Summary

a. Provide a brief (2-3 sentences) lay language synopsis of the study. Include an explanatory sentence about the study article (*e.g., product X is a compound that increases excretion of salt and therefore may be of use in the treatment of high blood pressure*)

- Gastric point of care ultrasound (G-POCUS) can show if a postoperative patient’s stomach is empty or full, and a full stomach has been correlated with delayed return of bowel function after surgery, longer time to GI-3 recovery (defined as the ability to tolerate a regular diet and have either flatus or bowel movement), and increased length of stay. In the study group, patients will have a gastric POCUS exam at 0600 on post-operative day 1 and daily thereafter until they have return of bowel function whereas in the control group, patients will receive standard postoperative care without the addition of any G-POCUS exams. In the study group, the results of the G-POCUS exams will be employed in a care algorithm designed to help clinicians decide how to advance patients’ diets and when to place and remove nasogastric tubes (NGT).

2. Objectives and Significance

a. State the primary objective(s) of the study.

- Determine if using G-POCUS as a clinical decision-making tool reduces rates of aspiration pneumonia/pneumonitis, length of hospital stay, need for additional/unplanned procedures in the patient population.

b. State the secondary objectives(s) of the study.

- Secondary: Determine if G-POCUS can be used to develop clinical practice guidelines for when to advance/de-escalate diets postoperatively and when to insert/remove NGTs in patients who are recovering from abdominal/colorectal surgery.

c. What benefit or knowledge will be gained?

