- This study builds on the findings of our preliminary studies, which showed that a full stomach on handheld G-POCUS exam on postoperative day one was correlated with longer length of stay, increased incidence of delayed bowel function (DBF), emesis, and nasogastric tube placement. It will help determine if G-POCUS can be

47 used as an objective clinical decision-making tool for postoperative patients.
48 Ultimately, we hope that integrating G-POCUS exams into the clinical workflow
49 will help reduce rates of DBF, ileus, and aspiration pneumonia.
50

51 d. State hypothesis you are testing.

- 52 • We hypothesize that G-POCUS can be used as an objective measure to diagnose
53 delayed bowel function after surgery, and consequently reduce the serious
54 complication associated with impaired return of bowel function.
55

56 3. Briefly describe the background and rationale for the research in lay language. Please limit
57 response to one paragraph. State the perceived problem and why it is being investigated. (*Do*
58 *not include references and please do not cut and paste grant application or review articles.*
59 *“See investigator brochure” is not an acceptable response.*)
60

61 Delayed bowel function (DBF) and postoperative ileus (POI), or disruption of the normal
62 forward peristaltic bowel activity after abdominal surgery are common complications in
63 general surgery patients that can lead to nausea, emesis, bowel perforation, or aspiration
64 pneumonitis. DBF and POI increase length of stay, morbidity, and mortality in general
65 surgery patients. It is extremely difficult to predict who will develop DBF and POI. Further,
66 diagnosing patients with postoperative DBF or POI is almost entirely based upon clinical
67 acumen, history, and physical exam. To date no imaging or laboratory studies are specifically
68 recommended to diagnose these complications.

69 Gastric Point of Care Ultrasound (G-POCUS) is a simple and reliable imaging modality that
70 can be performed at the bedside and does not involve ionizing radiation. In our pilot study, we
71 hypothesized that G-POCUS volume (ie: whether a patient’s stomach appears full or empty)
72 would correlate with measures of delayed bowel functioning based on identification of full
73 versus empty stomach postoperatively following colorectal surgery. To test this hypothesis,
74 we performed a small pilot study and found that patients with full stomachs had a higher

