117 Hospital, and Abington Hospital.
- 118 c. Data analysis: *(Provide statistical design for primary endpoint only. Please*
119 *indicate how the study is powered and what statistical tool(s) will be applied.*
120 *Please do not cut and paste entire statistical section from the sponsor protocol.*
121 *Pilot studies do not require a statistical plan but need to outline how the results*
122 *will be used to power future studies.)*
123
- 124 • Sample size = 128 participants
125 80% power using 2-sided t test – would require 64 patients per group (128 total)
126 to show a 25% decrease in time to GI3 recovery in G-POCUS group vs standard
127 care group.
- 128 Sample size calculation was performed using a continuous variable as the primary
129 endpoint (number of days to GI-3 recovery), and assuming an alpha of 0.05 and a
130 power of 80%. Results from the pilot study were used to inform sample size
131 calculation. All patients in the pilot study took on average 1.5 days (SD 1-3 days)
132 to reach GI-3 recovery, while patients in the pilot study with empty stomachs on
133 G-POCUS on POD1, took 1 day on average (SD 1-2) to reach GI-3 recovery.
- 134 d. If the protocol involves sending tissue to a commercial entity, please certify that
135 the following criteria are met (see TJU policy #110.17, "Collection, storage, use
136 and distribution of tissue for research purposes"). Also, please provide a copy of
137 the sponsor contract/agreement or an e-mail from ORA certifying same. The PI
138 certifies that he or she (check applicable statements):

- Will have significant input into the study design and/or conduct of the study.
- Will receive experimental data and participate in data analysis.
- Has established the right to be a co-author on any publications related to this protocol.
- Certifies that Jefferson ORA is negotiating a sponsored research agreement, to be signed prior to work commencing.

5. Delineate procedures that are standard of care from those that are being performed specifically for the research. *Delete examples and add additional rows to table as appropriate. Provide the information to the best of your ability.*

Procedure	Research	Standard of Care
G-POCUS on POD1	X	
G-POCUS on POD 2-5, if criteria met	X	

6. Describe the Data and Safety Monitoring Plan (DSMP) for this protocol. See OHR Policy G 616 for guidance.

 X Study is minimal risk and does not require a DSMP. Accuracy of data will be confirmed by PI before study is locked.

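### The primary objective (aspiration, length of stay, unplanned procedures) does not match the primary endpoint for which the trial is sized (days to GI-3 recovery)

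*Protocol*

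**What the plan says.** - **Part A, item 2a (primary objective).** The trial is to determine whether using G-POCUS for decisions "reduces rates of aspiration pneumonia/pneumonitis, length of hospital stay, need for additional/unplanned procedures in the patient population". The three outcomes are not ranked, and no rate, standard deviation or target difference is given for any of them, here or elsewhere.
- **Part A, item 2b (secondary objective).** "Secondary: Determine if G-POCUS can be used to develop clinical practice guidelines for when to advance/de-escalate diets postoperatively and when to insert/remove NGTs in" patients recovering from this surgery. GI-3 recovery is not mentioned.
- **Part A, item 2d (hypothesis).** "We hypothesize that G-POCUS can be used as an objective measure to diagnose" delayed bowel function and so reduce its serious consequences. GI-3 recovery is not mentioned.
- **Part A, item 4c (data analysis).** The form asks here for the design for the primary endpoint only. The answer reads "Sample size calculation was performed using a continuous variable as the primary" and continues "endpoint (number of days to GI-3 recovery), and assuming an alpha of 0.05 and a" power of 80%. The size is given as "80% power using 2-sided t test – would require 64 patients per group (128 total") "to show a 25% decrease in time to GI3 recovery in G-POCUS group vs standard" care.
- **Elsewhere.** GI-3 recovery is defined in the lay summary (item 1a), where a longer time to it is one of the correlates of a full stomach. Item 4b speaks of primary and secondary outcomes but does not list them.

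**The concern.** The objective says what question the trial is to answer, and the primary endpoint is the measurement that answers it. Here they are different outcomes. A clear benefit on days to GI-3 recovery would leave the stated primary objective unanswered. A finding of no difference on aspiration or unplanned procedures would address the objective, but in a trial not sized to detect one. A reader of the final report could also not tell from the protocol whether success is to be judged by item 2a or by item 4c.

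This is not detail that a statistical analysis plan would normally supply. The protocol itself fixes both the objective and the primary endpoint, and the two disagree.

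**Working it through.** **1. The plan's own figure.** Inputs from item 4c: two-sided t test, alpha 0.05, power 80%, 64 per group. By the normal approximation, n per group = 2(1.960 + 0.842)² / d², where d is the difference divided by the SD. With d = 0.5 this is 2 × 7.85 / 0.25 = 62.8, so 63; the noncentral t gives 64. The stated size is therefore that for a difference of 0.5 SD, and it was derived for days to GI-3 recovery only.

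**2. Aspiration at 64 per arm.** The protocol gives no rate, so the control rates are assumptions. Power = sum over all event counts (a, b) of P(a | 64, p) × P(b | 64, p/2), counting the tables where the two-sided Fisher test gives p ≤ 0.05 in favour of G-POCUS.

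| Assumed control rate | Halved to | Expected control events (64 × rate) | Exact Fisher power |
|---|---|---|---|
| 2% | 1% | 1.3 | 0.1% |
| 5% | 2.5% | 3.2 | 2.5% |
| 10% | 5% | 6.4 | 9.8% |

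Fisher's test is conservative with few events. The normal approximation gives 7%, 11% and 19% for the same rows, and 2319, 906 and 435 per arm for 80% power. One check needs no assumed rate: with no events at all under G-POCUS, 5 control events give p = 0.058 and 6 give p = 0.028. Even complete elimination reaches significance only if at least 6 of 64 controls (9.4%) aspirate.

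**3. Unplanned procedures at 64 per arm.** Same method, rates again assumed.

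| Assumed control rate | Halved to | Exact Fisher power | Normal approximation |
|---|---|---|---|
| 20% | 10% | 27% | 35% |
| 30% | 15% | 45% | 53% |

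**4. Length of stay at 64 per arm.** The difference detectable with 80% power is 0.50 SD (noncentral t). The protocol gives no SD. For a 1-day difference, power is 80%, 46% and 29% at assumed SDs of 2, 3 and 4 days.

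**5. Multiplicity, as a conditional bound.** If the three outcomes in item 2a were each tested at 0.05 and any one counted as success, the familywise error under independence would be 1 − 0.95³ = 14.3%. The protocol states no such rule. Positive correlation lowers the figure, and so do exact tests: the actual size of Fisher's test at 64 per arm is about 1.2% at a 5% event rate and 2.3% at 10%. With those two sizes and a 5% test on length of stay, the figure is 1 − 0.95 × 0.988 × 0.977 = 8.3%.

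**The case against.** The strongest reply is that item 4c does fix the primary analysis: one endpoint, one test, one alpha and one power. That stands. A reader might infer from item 2a that the trial has no single primary endpoint, or that any of four outcomes could be declared primary afterwards. The document does not support that; the fault is that the objective and the endpoint disagree.

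A reader might also infer a false-positive rate of 14%, or more with GI-3 recovery as a further candidate. That needs a rule under which any one outcome wins, and independent outcomes. The protocol states alpha 0.05 only for GI-3 recovery, and its own background links delayed bowel function with length of stay and aspiration. Handling of further outcomes may also properly sit in a statistical analysis plan. The 14% is a conditional figure, not a property of this design.

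Nor is it right that the trial has no power for anything in item 2a. Length of stay would have 80% power for a 0.5 SD difference; what is missing is any calculation for it. That aspiration is rare is likewise an assumption here, since the protocol gives no rate. Finally, the form allows more than one primary objective, so listing several is not in itself an error.

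None of this removes the mismatch. The outcome on which the trial is sized is still absent from every objective and from the hypothesis.

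**Conclusion.** The point holds as an internal contradiction. Item 2a makes three unranked outcomes the primary objective, while item 4c makes a fourth the primary endpoint and sizes the trial on it alone. The result on the powered endpoint therefore does not answer the primary objective as stated.

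The contradiction rests on the text alone. Its practical size rests on assumed control rates and on halving as the target effect. Over the ranges shown, 64 per arm gives about 0.1% to 10% exact power for aspiration and 27% to 45% for unplanned procedures. For length of stay it is adequate only if the true difference is about half a standard deviation. A non-significant result on either binary outcome would say little.

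It should be corrected, because it decides what the trial may conclude.

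**What to change.** Reconcile item 2a with item 4c before outcome data are seen.

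- **Cheapest route.** Make the effect of the G-POCUS strategy on time to GI-3 recovery the single primary objective. Move length of stay, unplanned procedures and aspiration to the secondary objectives in item 2b. Report aspiration descriptively, with a confidence interval and no efficacy claim. Bring the hypothesis in item 2d into line. This is an amendment of wording; the realignment itself adds no patients and no procedures.
- **Alternative.** Keep one of the three outcomes in item 2a as primary, name it as the primary endpoint in item 4c, and redo the sample size with a stated rate or SD and target difference. For either binary outcome this would probably mean a larger trial: over the assumed rates above, the normal approximation asks for 435 to 2319 per arm to halve aspiration, and 199 or 121 per arm to halve unplanned procedures from 20% or 30%.

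Neither route settles a separate matter in item 4c. The stated 64 per group fits 0.5 SD, for example 1.5 against 1.0 day with SD 1, which is a 33% decrease (0.5 / 1.5). The stated 25% decrease is 0.25 × 1.5 = 0.375 day, and at SD 1 it has about 56% power with 64 per group. The pilot spread is printed as a range ("All patients in the pilot study took on average 1.5 days (SD 1-3 days"), so the SD actually used is not known. Those inputs need their own correction, which may change the sample size.

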75 incidence of DBF, length of stay, emesis, and need for NGT placement.
76

77 4. Briefly describe the research design. (*Use charts and flow diagrams if applicable.* “*See*
78 *protocol” is not an acceptable response.*)
79

80 a. Subjects: State inclusion and exclusion criteria.

81 • Inclusion criteria:

- 82 ○ Completed signed and dated informed consent form
- 83 ○ Willing to comply with all study procedures
- 84 ○ Male or female, 18 years of age or older
- 85 ○ Presenting for a schedule elective colorectal/abdominal surgery, either open
86 or laparoscopic

87 • Exclusion criteria:

- 88 ○ History of gastroparesis or known gastric/intestinal motility disorder
- 89 ○ History of gastric/bariatric surgery
- 90 ○ Intubated/sedated postoperatively
- 91 ○ Presence of open abdominal wounds (including abdominal wound vac)
- 92 ○ Patients who received a complex abdominal wall reconstruction
- 93 ○ Class III/IV Wound (Contaminated/Infected/Dirty)

- 94 ○ Surgery was emergent/urgent/unscheduled
95 ○ NGT placed or present at time of operation
96 ○ Presence of ileostomy/colostomy
97 ○ J-pouch reconstruction patients
98 ○ Currently pregnant patients
99 ○ Patients aged <18 years old
100
101 b. Procedures: Provide study visit details.
- 102 • This will be a randomized single-blinded study of handheld G-POCUS in which
103 our study population will be inpatients hospitalized after abdominal/colorectal
104 surgery at TJUH, Methodist Hospital, or Abington Hospital. Patients will be
105 randomized to an unblinded intervention arm or an unblinded standard of care
106 arm. On POD1, patients will be asked if they are having any GI symptoms. These
107 are defined as presence of nausea, emesis, belching, and/or hiccups. In the
108 intervention arm, clinicians will use the results of G-POCUS and
109 presence/absence of GI symptoms to inform decision making according to one of
110 two standardized algorithms (see Appendix). In the control arm, presence of GI
111 symptoms will be assessed, and once of two standardized algorithms which are
112 representative of the current standard of care for postoperative diet management.
113 Data from both groups will be used to determine if the G-POCUS studies' results
114 can predict the incidence of primary or secondary outcomes (control) or if
115 intervening on results of G-POCUS can decrease the incidence of undesirable
116 outcomes. This will be a multicenter study enrolling patients at TJUH, Methodist

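### Objective 2b looks for rules on diet and nasogastric tubes, but the design can test the scan-based algorithm only as a whole, and the control-arm prediction aim has no scan data under section 1a

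*Protocol*

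**What the plan says.** Protocol Part A, 2b gives the secondary objective: "Determine if G-POCUS can be used to develop clinical practice guidelines for when to advance/de-escalate diets postoperatively and when to insert/remove NGTs".

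Part A, 1a describes the two arms. In the study group "the results of the G-POCUS exams will be employed in a care algorithm designed to help clinicians decide how to advance" diets and when to place and remove NGTs. By contrast, "in the control group, patients will receive standard postoperative care without the addition of any G-POCUS exams". The same section defines GI-3 recovery as tolerating a regular diet plus flatus or a bowel movement.

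Part A, 4b adds that, in the "intervention arm, clinicians will use the results of G-POCUS and" "presence/absence of GI symptoms to inform decision making according to one of" two standardised algorithms. Controls are managed by symptom-based algorithms that represent current care. The section then states two uses of the data. The first reads, across two lines, "Data from both groups will be used to determine if the G-POCUS studies' results" "can predict the incidence of primary or secondary outcomes (control) or if". The second asks whether acting on the scan reduces undesirable outcomes.

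The algorithms are in the Appendix, as a figure that is not available in the text reviewed.

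**The concern.** A guideline on when to advance a diet or place a tube needs evidence on what happens to patients with the same scan result under different actions. The trial randomises between two complete care algorithms, and only one of them uses a scan. The patients with a scan result are the patients whose diet and NGT care is informed by it.

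Two things are at stake. First, 2b is worded more broadly than a comparison of packages can support. A favourable result would endorse the algorithm as written, without saying which of its steps or cut-offs did the work. Second, 4b plans to ask whether scan results predict outcomes and marks that question for the control arm. If controls are not scanned, the only scan-outcome data come from the arm where clinicians act on the result, and there the association reflects both the scan and the response to it.

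**Working it through.** The plan gives no figure for 2b. The sample size in 4c was set for days to GI-3 recovery, and it is used here only to count patients.

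**Inputs**
- 64 patients per group, 128 in total (4c).
- Scans in the control arm: none (1a).
- Scans in the study arm: POD1 and daily thereafter until return of bowel function (1a), used with GI symptoms (4b).

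**Step 1: who has a scan result.** Study arm 64, control arm 0, so 64 of 128. Scanned patients randomised to a different management for the same scan result: 0 of 64. Scan-outcome pairs for a control-arm prediction analysis: 0 of 64.

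**Step 2: can the scan and the action be separated within the study arm?** Suppose, as an assumption, that the action is a fixed function of the scan. A model with an intercept, the scan result and the action then has three columns but rank 2, so the two effects cannot be told apart. If symptoms also change the action, patients with the same scan result do receive different care, but they differ in symptoms too. Symptoms such as nausea and emesis are themselves likely to be prognostic, so that contrast is confounded.

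**Step 3: would departures from the algorithm help?** The protocol gives neither the share of full stomachs nor the rate of departures. Assume 30% to 50% full stomachs and 5% to 20% departures:
- low end: 64 × 0.30 × 0.05 = 0.96, about 1 patient;
- high end: 64 × 0.50 × 0.20 = 6.4, about 6 patients.

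These few patients would be selected by clinical judgement, not by randomisation.

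**Step 4: what acting on the scan does to the association.** If the response to a full stomach prevents emesis, the link between full stomach and emesis weakens. If the algorithm holds back a diet step after some scans, GI-3 comes later for those patients partly by definition, because GI-3 requires a regular diet. The two mechanisms pull in opposite directions. Without the Appendix figure neither can be confirmed or sized.

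**Step 5: sections 1a and 4b side by side.** Section 1a excludes control scans. Section 4b marks the prediction question for control. The procedures table in Part A, 5 lists G-POCUS on POD1, and on POD 2-5 if criteria are met, without naming an arm, so it does not settle the matter.

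**The case against.** The strongest reply is that 2b asks only whether G-POCUS can be used to develop guidelines. It does not promise thresholds or a comparison of actions within a scan result. Randomising a scan-based algorithm against a symptom-based one is a reasonable test of whether such a guideline works, and 4b states that aim separately. This stands in part: the between-arm result does bear on 2b, and the remedy below relies on it. It does not rescue the wording, which speaks of when to take each of four actions.

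A second reply is that 4b may imply that controls are scanned with results withheld. If so, the control-arm association would be free of action on the scan, and the two algorithms could be compared among patients with the same first scan, although still as packages. Section 1a rules this out as written, so the reply exposes a contradiction and does not remove the problem.

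A third reply is that labelling an association as descriptive usually belongs in the SAP, which is not shown. That is fair for analysis detail. The objective and the planned use of the data, however, are stated in the protocol, and no later analysis can supply control scans that were never taken.

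Some stronger readings are tempting and are not supported:
- A reader might infer that the scan alone dictates care. The text says that it helps clinicians decide and that, with symptoms, it informs decisions.
- A reader might infer a diet delay of fixed length after a full scan, or a distortion of known size. No visible rule says so.
- A reader might take the gap between the pilot means in 4c (1.5 and 1 day) as a yardstick for the distortion. Those means compare all patients with the empty-stomach subgroup, not full with empty.
- A reader might infer that the investigators will set rules from study-arm associations. The protocol does not say that; it merely leaves it open.

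**Conclusion.** The point holds as a limit on what the secondary objective can conclude. With no control scans, as 1a states, the trial can show whether the scan-plus-symptom algorithm as a package outperforms the symptom-only algorithm. It cannot show which action suits which scan result, since 0 of the 64 scanned patients are randomised to an alternative. The control-arm prediction aim in 4b has no data under 1a, and the two sections conflict. Study-arm associations between scan and outcome are altered by the care that followed the scan, by an amount and in a direction that the documents do not allow one to state.

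It would be too strong to say that the trial tells nothing about 2b, because the randomised comparison of the two algorithms remains valid. The conclusion rests on the text of 1a about control scans. If controls are in fact to be scanned with results withheld, the prediction aim becomes feasible. The limit on choosing between individual actions remains.

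**What to change.** 1. Restate 2b as a comparison of the two algorithms, as randomised, on NGT placement, diet de-escalation and emesis.
2. Reconcile 1a and 4b on whether controls are scanned, and name the arm in the procedures table in Part A, 5. If controls are not scanned, delete the control-arm prediction aim from 4b.
3. Add to 4b that scan-outcome associations within the study arm are descriptive, apply only under algorithm-guided care and will not be used to set decision rules. Where they are shown, report time to first flatus or stool alongside GI-3, because GI-3 contains a diet component that the algorithm steers. Flatus or stool timing may still be affected by the care given, so this makes the display clearer without removing the problem.

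The cost is small. Part A, 7 already lists diet at times of evaluation, need for NGT placement and patient-reported symptoms. Flatus or stool is already needed to determine GI-3, but its timing is not listed separately in Part A, 7, so a data field should be confirmed. The same applies to emesis after POD1, because 4b describes the symptom question for POD1 only. No extra patients are needed. The downside is a more modest secondary claim.

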503 simplified consent form (e.g., OHR-8C) and/or the surrogate consent form (OHR-8B).
504 • No
505
- 506 12. Will the potential subject be informed of the research or be provided a copy of the consent to
507 review prior to the actual time of consent? If so, how much time in advance? How much time
508 will be available for the consent process?
509 • Patients will be provided a copy of the consent at the initial office visit. Typically,
510 patients are seen in the office 2 to 3 weeks prior to their scheduled operation. Patients
511 will be afforded time during the initial office visit to review the consent form and ask
512 questions. Patients will be informed that they can provide consent at that point or at any
513 point up until two weeks before their operation. They will be informed that if they are
514 undecided, need additional time to review the consent, need additional time to reach a
515 decision, or would like to further discuss the study with one of the investigators or the
516 study coordinator, then appropriate arrangements will be made.
517
518
- 519 13. What provisions will be made if the potential subject does not wish to proceed with the consent
520 interview at the first encounter?

- 521 • Patients will not be approached additional times after the first encounter. They will be
522 informed that they may contact the PI or co-investigators and further discuss participation
523 at any time after the initial interview if they so wish. Patients will receive the same
524 standard of care despite their decision to participate or not.
525

526 14. Is surrogate consent involved? YES _____ NO X

527
528 15. Will subjects be paid or receive any other inducements for participating? If yes, please explain.
529 *Please note that payment of subjects must be on a pro-rated basis unless there are compelling*
530 *reasons not to prorate. There cannot be a requirement to finish all visits in order for subjects*
531 *to be paid, as this is considered coercive.*

- 532 • No
533

534 16. Describe any steps taken to minimize the possibility of coercion or undue influence.

- 535 • Voluntary participation will be stressed. The ability of patients to have colorectal surgery
536 at Jefferson without participating in any research protocols and still be treated at the same
537 high level as all of our patients will be emphasized. Patients will also be aware that they
538 can stop study participation at any time they wish.
539

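### The planning figures come from a colorectal pilot, but the trial enrols colorectal and other abdominal surgery, and the protocol does not show that the figures carry over

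*Protocol*

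**What the plan says.** **Pilot.** Protocol Part A, item 3 frames the pilot question as full "versus empty stomach postoperatively following colorectal surgery. To test this hypothesis". The pilot is described in no other surgical population, and its eligibility criteria are not given.

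**Sample size.** Part A, 4c takes its inputs from that pilot: "calculation. All patients in the pilot study took on average 1.5 days (SD 1-3 days"). For patients with an empty stomach on POD1 it gives 1 day, with the SD printed as 1-2. The plan is 64 per group (128 in total), a two-sided t test, alpha 0.05 and 80% power for a 25% shorter time to GI-3.

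**Trial population.** Part A, 4a admits patients "Presenting for a schedule elective colorectal/abdominal surgery, either open" or laparoscopic. Part A, 4b adds that "our study population will be inpatients hospitalized after abdominal/colorectal" surgery. The exclusions narrow this, for example "Patients who received a complex abdominal wall reconstruction" and "Presence of ileostomy/colostomy". No list says which non-colorectal procedures qualify.

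**Wording elsewhere.** The secondary objective (Part A, 2b) covers both abdominal and colorectal surgery. Part F, item 16 mentions only one of them: "Voluntary participation will be stressed. The ability of patients to have colorectal surgery". Item 3 says that disruptions of "forward peristaltic bowel activity after abdominal surgery are common complications in" general surgery patients, and gives no rate by procedure.

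**The concern.** A sample size taken from a pilot holds only if the pilot's mean, spread and effect carry over to the patients who will be randomised. Here the pilot is colorectal and the trial is wider, and no sentence justifies the transfer. Time to GI-3 (regular diet tolerated, plus flatus or stool) could plausibly have a different mean and SD after non-colorectal operations, and G-POCUS could have a different effect there.

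If some enrolled patients had no room to benefit, the average effect would be smaller than planned and 64 per group would give less than 80% power. If operation type is prognostic, an unadjusted comparison also leaves its variation in the error term. The colorectal patients, for whom the pilot evidence exists, would have no estimate of their own. The differing descriptions of the population also leave three hospitals to decide for themselves how wide the criterion is.

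**Working it through.** **Step 1: reproduce 64 per group.** With the normal approximation, n per group = 2(z₀.₉₇₅ + z₀.₈₀)² / d², where d is the mean difference divided by the SD. For d = 0.5 this is 2(1.960 + 0.842)² / 0.25 = 62.8, so 63. The exact t-test calculation gives 64, with power 80.1%. The plan therefore implies d = 0.5.

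**Step 2: see whether the printed inputs give d = 0.5.**
- A 25% reduction from 1.5 days is 0.25 × 1.5 = 0.375 day. For d = 0.5 the SD must be 0.375 / 0.5 = 0.75, below the printed range of 1-3.
- With 0.375 day and SD 1, d = 0.375. Power at 64 per group is then 55.8%, and 113 per group would be needed for 80%.
- The contrast 1.5 versus 1 day with SD 1 does give d = 0.5 and 64 per group, but that is a reduction of 0.5 / 1.5 = 33%, not 25%.

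This is a separate defect of 4c. It matters here because the 80% below is a nominal starting point that the printed inputs do not establish.

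**Step 3: illustrate a failed transfer.** Assume a share f of patients cannot benefit, the planned effect holds in the rest, and the SD is unchanged. Then d = 0.5(1 − f), and the required n grows by 1/(1 − f)². The protocol does not give f. Exact t-test results:

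| Assumed f | d | Power, 64 per group | n per group for 80% |
|---|---|---|---|
| 0% | 0.50 | 80.1% | 64 |
| 10% | 0.45 | 71.4% | 79 |
| 20% | 0.40 | 61.2% | 100 |
| 30% | 0.35 | 50.2% | 130 |

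**Step 4: vary the SD assumption.** Suppose those patients have half the SD and the same mean. At f = 10% the pooled SD is √(0.9 + 0.1 × 0.25) = 0.962 of the original, d = 0.45 / 0.962 = 0.468, and power is 74.7% instead of 71.4%. At f = 25% it is 64.6% instead of 55.8%. The result depends on inputs that the protocol does not give.

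**Step 5: size of chance imbalance.** If 30% of patients had other abdominal surgery (again an assumption), the difference in that share between two arms of 64 has a standard error of √(2 × 0.3 × 0.7 / 64) = 0.081. Without stratification, gaps of up to about 1.96 × 0.081 = 16 percentage points would be unremarkable.

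**The case against.** The strongest reply is that nothing in the protocol shows the added patients to be different. Item 3 calls delayed bowel function and ileus common after abdominal surgery and hard to predict. The population is inpatients assessed on POD1, and several exclusions narrow it. Early recovery is not peculiar to non-colorectal surgery either: in the colorectal pilot itself, empty-stomach patients averaged 1 day to GI-3. Breadth is also deliberate, since the secondary objective names both kinds of surgery.

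All of this stands. A reader might infer that any elective abdominal operation is admitted, that the extra patients carry little risk, and that they dilute the effect so that the pilot figures no longer describe the trial. The documents do not support that reading. They give no case mix, no risk by procedure and no pilot eligibility criteria, so one can say only that the figures are not shown to apply.

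A second reply is that stratification and adjustment often belong in an SAP or randomisation plan, which may exist, and that chance imbalance is not bias and is already covered by the t test's error rate. That is correct. Their absence from this form is therefore not counted as an error; they are offered as an inexpensive improvement on the t test that 4c names. The mismatch between the source of the inputs and the eligibility criterion lies in the protocol text itself, and these replies do not remove it.

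**Conclusion.** The point holds in a limited form. The GI-3 planning inputs come from a colorectal pilot, eligibility is wider, Part F describes the operation as colorectal only, and no justification links them. The loss of power, if any, cannot be derived from the protocol. The figures of about 71% and 61% rest on assumed shares of 10% and 20% who cannot benefit, an unchanged SD, and a starting effect of 0.5 that the printed 25% and SD range do not themselves produce. They show sensitivity and are not an estimate. Low-risk patients could lower the mean, the effect and the SD together.

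The documents do not support requiring a colorectal-only trial or a minimum expected stay. The first would leave the abdominal part of the secondary objective untested. Whether the second would match the pilot cannot be checked. Both are design trade-offs for the sponsor.

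**What to change.** 1. Keep the broad population. Stratify randomisation by planned operation, colorectal versus other abdominal, with a one-line definition of the two strata. The planned operation is known before surgery.
2. In 4c, replace the unadjusted t test with a GI-3 comparison adjusted for that factor, for example a linear model with terms for arm and stratum. Pre-specify the colorectal stratum as a secondary estimate.
3. State in 4c that the planning mean, SD and effect come from colorectal patients only.
4. Reconcile the population wording in Part A, 4a and 4b with Part F, item 16.

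The cost is one extra stratification factor and a few lines of text. The enrolled population and the target of 128 do not change on account of this point. The inconsistency between the 25% reduction, the printed SDs and 64 per group needs its own correction.
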